3. BLINDING AND RANDOMIZATION METHODS

The once-weekly lonapegsomatropin and once-weekly placebo treatment arms will be double-blinded, whereas the daily somatropin product treatment arm will be open-label.

To maintain the double-blind between the once-weekly lonapegsomatropin and once-weekly placebo treatment arms, subjects in the once-weekly placebo treatment arm will receive the same dose volume as if they would have been randomized to once-weekly lonapegsomatropin. The placebo will look similar to lonapegsomatropin: the same vials, cap color and diluent will be used, and a blinding shell cover the glass vial.

Eligible subjects will be enrolled in the trial and sequentially assigned an identification number. A randomization schedule will be developed by an independent party to maintain blinding. Approximately 240 subjects will be randomized in a 1:1:1 ratio and assigned to a treatment sequence group via an Interactive Web Randomization System (IWRS).

For dose adjustments due to IGF-1 that are required for the lonapegsomatropin arm, a sham titration will be initiated for a subject in the placebo arm in a pattern that follows the dose modifications of the lonapegsomatropin arm. In case of high IGF-1 values, a dose titration/reduction recommendation based on a predetermined algorithm will be provided by the unblinded team member. Refer to the trial blinding and dose adjustment plan for details.

Blinding of a weekly trial drug (lonapegsomatropin or placebo) versus daily comparator is not considered feasible. However, to protect the integrity of the trial, critical assessors (selected Sponsor team members, central vendors and other personnel as appropriate and feasible) will be blinded to all treatment assignment to minimize potential bias prior to database lock and trial unblinding. Refer to the trial data handling plan for details.

The central reader for DXA scans will be blinded to the treatment arm throughout the trial.

Staff working with the PK vendor, clinical trial supply and unblinded team members will be unblinded throughout the trial conduct. Refer to the blinding plan for details.

4. STUDY OBJECTIVES

4.1. PRIMARY OBJECTIVE

To evaluate the efficacy of once-weekly lonapegsomatropin compared to placebo at 38 weeks in adults with GHD.

4.2. SECONDARY OBJECTIVES

1. To evaluate the safety and tolerability of once-weekly lonapegsomatropin in adults with GHD.
2. To evaluate the PK of once-weekly lonapegsomatropin in adults with GHD.
3. To evaluate the PD of once-weekly lonapegsomatropin in adults with GHD.

4.3. TERTIARY OBJECTIVE

5. SAMPLE SIZE CONSIDERATIONS

This trial is powered for the efficacy comparison of lonapegsomatropin versus placebo. The daily somatropin product arm is included as a calibration arm and not powered for formal comparison.

Approximately 240 subjects will be randomized in a 1:1:1 ratio to once-weekly lonapegsomatropin, once-weekly placebo, or daily somatropin. However, for local regulatory requirements, recruitment may be kept open in some countries after having this number reached for the global trial.

A sample size of 80 subjects per arm in the lonapegsomatropin and placebo once-weekly treatment arms will provide 90% power to detect a treatment difference of 1.9% between once-weekly lonapegsomatropin and placebo for the primary endpoint of change from baseline in trunk percent fat at Week 38 at the 2 sided 5% significance level, with the assumption of a common SD of 3.7%.

Sample size and power calculations were performed using the software SAS v 9.4.

6. PLANNED ANALYSIS

6.1. INTERIM ANALYSIS

No interim efficacy analysis for the main period is planned for this trial.

6.2. FINAL ANALYSIS

The final analysis of the trial will be conducted after the data base lock when all randomized subjects have completed 38 weeks of treatment or discontinued early.

7. DATA MONITORING COMMITTEE

Not applicable

8. ANALYSIS ENDPOINTS

8.1. EFFICACY ENDPOINTS

8.1.1. Primary Efficacy Endpoint

- Change from baseline in trunk percent fat (as assessed by DXA) at Week 38.

8.1.2. Key Secondary Efficacy Endpoints

- Change from baseline in trunk fat mass at Week 38 (as assessed by DXA)
- Change from baseline in total body lean mass at Week 38 (as assessed by DXA)

[figure not shown]
[figure not shown]
8.2. OTHER SECONDARY ENDPOINTS:**8.2.1. Safety Endpoints**

Safety endpoints as measured throughout the 38 weeks of treatment include:

- Incidence of AEs
- Laboratory values
- Vital signs
- Incidence of ADA and neutralizing antibodies against hGH
- ECGs
- Fundoscopy

8.2.2. Other Secondary Endpoint: Pharmacokinetic/Pharmacodynamic Endpoints

- hGH levels
- Lonapegsomatropin levels
- mPEG levels
- IGF-1 levels and IGF-1 SDS
- IGFBP-3 levels and IGFBP-3 SDS

8.3. TERTIARY ENDPOINTS**8.4. EXPLORATORY ENDPOINTS**

9. DEFINITIONS

9.1. DATE OF FIRST DOSE AND DATE OF LAST DOSE OF TRIAL DRUG

The date of the first dose of randomized trial drug is defined as the date when a subject receives the first dose of randomized trial drug. The date of the last dose of randomized trial drug during the 38 weeks of treatment is defined as the date a subject receives the last dose of randomized trial drug. If the complete date of last dose of trial drug is unknown, the last date the randomized trial drug was known to have been taken will be used.

The baseline value is defined as the last measurement on or before the first administration date (if time is not available) of the trial drug, unless otherwise specified.

9.2. STUDY DAY

Study day will be calculated with respect to the date of the first dose of trial drug (Study Day 1). For assessments conducted on or after the date of the first dose of trial drug, study day will be calculated as:

$$(\text{Assessment date} - \text{date of first dose of trial drug}) + 1$$

For assessments conducted before the date (and time) of the first dose of trial drug, study day will be calculated as:

$$(\text{Assessment date} - \text{date of first dose of trial drug})$$

For subjects who do not receive any amount of trial drug, study day will be calculated as above with respect to the date of randomization.

9.3. DURATION OF TREATMENT AND COMPLIANCE

Treatment duration is defined as the duration of time from the date of the first dose of trial drug to the date of the last dose of trial drug as follows:

Lonapegsomatropin:

Duration of treatment (day) = Last dose date of lonapegsomatropin – first dose date of lonapegsomatropin + 7

Treatment compliance = number of actual doses taken/total number of planned doses, where the total number of planned doses = Duration of lonapegsomatropin treatment/7

Placebo:

Duration of treatment (day) = [(Last dose date of Placebo – first dose date of Placebo + 7)

Treatment compliance = number of actual doses taken/total number of planned doses, where the total number of planned doses = Duration of Placebo/7

Daily somatropin:

Duration of treatment (day) = Last dose date of Daily somatropin – first dose date of Daily somatropin + 1

Treatment compliance = number of actual doses taken/total number of planned doses, where total number of planned doses = Duration of Daily somatropin treatment during the trial

9.4. AGE

Unless otherwise specified, the age will be the integer value of the derived value which will be based on the informed consent date: $\text{Age} = (\text{Informed Consent Date} - \text{Birth Date})/365.25$, rounded down to the next integer. When the date of birth is missing, the age recorded on CRF at the screening visit will be used.

If birth date is missing and age recorded on CRF is also missing, the birth date will be imputed (see Section 11.2.1) before calculating the age.

For a specific measurement, Age (years) = (Date of measurement – Birth Date)/365.25 and Age (months) = (Date of measurement – Birth Date)/365.25*12.

9.5. BASELINE DXA MEASUREMENTS

The baseline value is defined as the last measurement on or before the first administration date (if time is not available) of the study drug, unless otherwise specified.

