
7. Subjects with prior cranial irradiation or hypothalamic-pituitary surgery: the procedure took place less than 12 months prior to screening.
8. eGFR <60 mL/min/1.73m² determined based on Modification of Diet in Renal Disease (MDRD) equation using serum creatinine from the central laboratory at screening.
9. Hepatic transaminases (ie, AST or ALT) >3 times the upper limit of normal according to the central laboratory at screening.
10. Heart failure NYHA class 3 or greater ([NYHA 1994](#)).
11. QTcF \geq 451 milliseconds on 12-lead ECG at screening.

Note: If the initial measurement is out of range, the assessment should be repeated 2 more times and the average QTcF value should be used to determine the subject's eligibility.

12. Poorly controlled hypertension, defined as supine systolic blood pressure >159 mmHg and/or supine diastolic blood pressure >95 mmHg at screening

Note: if the initial measurement is out of range, may be repeated 2 more times after 15 min and exclusion will be based on the average of the three measurements.

13. Cerebrovascular accident within 5 years prior to screening.
14. Anabolic steroids (other than gonadal steroid replacement therapy) or oral/intravenous/intramuscular corticosteroids (other than in replacement or stress doses as described in Inclusion Criterion No.5) within 90 days prior to or throughout screening.

Note: Stable doses of inhaled, intra-articular, or topical corticosteroids are permitted.

15. Currently using or have used within 26 weeks prior to screening any weight-loss or appetite-suppressive medications including orlistat, zonisamide, lorcaserin, bupropion, topiramate, sibutramine, stimulants (eg, phentermine or ADHD medications such as methylphenidate or amphetamines), GLP-1 receptor agonists (eg, dulaglutide, exenatide, liraglutide, lixisenatide, semaglutide), SGLT-2 inhibitors (eg, canagliflozin, dapagliflozin, empagliflozin, sotagliflozin) or medications that affects IGF-1 or GH measurements including cabergoline at doses above 0.5 mg weekly or bromocriptine at doses above 20 mg weekly.

Note: if it can be documented that no weight-loss occurred with these drugs, a 90-day withdrawal period prior to screening is sufficient.

16. Known history of hypersensitivity and/or idiosyncrasy to any of the test compounds (somatropin) or excipients employed in this trial.
17. Known history of neutralizing anti-hGH antibodies.
18. Inability to undergo scanning by DXA or a non-interpretable DXA scan at screening.

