10.2.1. Screening Period

The screening period will be used to collect clinical data to establish the subject's eligibility for the trial. Within the screening period, still missing assessments for inclusion / exclusion may be conducted. The following assessments will be performed, and appropriate data collected:

- Demography, including sex, age, childbearing potential, oral estrogen intake, ethnicity, and race
- Medical history, including a description of pituitary deficiencies
- Currently and previously taken relevant medications (for the 12 months prior to screening)
- Vital signs measurements
- Height and weight
- Physical examination
- Blood collection for the following laboratory assessments (fasting required; central analysis):
 - Routine chemistry and hematology (see Section 11.9)
 - Hormone status: TSH, fT4, fT3, and morning cortisol
 - Glycemic status: HbA1c, fasting insulin and fasting plasma glucose. In case of suspected glucose intolerance, a 2-hour oral glucose tolerance test should be performed
 - Fasting lipid panel
 - Females: Serum human chorionic gonadotropin (hCG)
 - Males: morning (6:00-10:00AM) serum total testosterone
 - IGF-1 and IGFBP-3

- ADA:
 - The ADA analyses may only be conducted after enrollment and are not required for eligibility verification. These data will be used to support evaluation of post-dose antibody detection
 - Blood samples for immunogenicity assessment will be retained for up to 5 years following trial finalization for possible further characterization if requested by the authorities of a potential anti-drug antibody responses
- 12-lead ECG, local reading
- Fundoscopy
- DXA scan (central reading)
- MRI / CT scan: A pituitary MRI scan is required at screening if an MRI scan from within 6 months prior to screening is not available. A CT scan can be used if MRI scan is contraindicated.

Screening shall be stopped at any point in case any of the eligibility criteria not being met, such cases will be classified as screening failures.

All results will be reviewed by the Medical Monitor to verify eligibility of each subject prior to randomization. Eligible subjects will be centrally randomized to 1 of 3 arms. Following randomization, it is recommended to start the Dose Titration Period (Visit 1) within 2 weeks from the time of randomization.

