Blood sampling for PK assessment	PK will be sampled on Visit 1 through Visit 7 in weekly treatment arms (lonapegsomatropin and placebo). PK will be sampled on Visits 1, 5 and 7 in daily somatropin treatment arm . PK analytes: hGH, lonapegsomatropin and mPEG will be analyzed at Visit 1 through Visit 7 in weekly lonapegsomatropin arm. PK analytes will not be analyzed in weekly placebo arm. PK analytes: hGH only, will be analyzed in daily somatropin arm. Data will not be distributed to the site staff.

Table 5: Treatment Period Procedures (Continued)

Assessment	Details and Comments
Samples for antibody assessment	At Visits 1, 2, 4, 6 and 7. Blood samples for immunogenicity assessment will be banked and may be used for additional characterization of ADA responses. Data will be reviewed by unblinded team member and results not routinely distributed to the site staff.
DXA scan	At Visits 1, 4 and 7; central reading. DXA scan at Visit 1 is not applicable for Germany. DXA assessments should be performed in a similar setting (+/- 2 hours compared to Visit 1 time, and similar hydration status) at each visit, using the same approved DXA machine throughout the trial. Body composition to be assessed at all DXA scans. Total body bone mineral content and bone mineral density to be assessed only at Visit 1. DXA assessment windows: Up to 1 week prior to Visit 1, pre-dose. Up to 1 week before or after Visit 4 (Weeks 11, 12, 13). Up to 1 week after Visit 7 (Week 38 or Week 39).
Study drug administration training	Visit 1 and as needed. Includes the training on the IFU (also provided to the subject for reference throughout the trial). Includes instructions that administration of study drug should occur at approximately the same time of day (for daily arm) and on the same day of the week (for weekly treatment arms) throughout the trial. Details regarding adjustment of a subject's dose day or dosing time are provided in the IMP Manual. Includes study drug administration by the site staff at Visit 1 (weekly treatment arms), and as needed.
Dose titration	Visits 2, 3 and 4. Subjects may also be instructed about new dose via phone. Unscheduled dose titrations may be communicated via phone.
Injection site reaction assessment	Visit 1 through Visit 7. At Visit 1, the investigator shall review the injection site at least 15minutes post-dose; at other visits all prior injection sites shall be examined. For documentation and reporting see Section 11.13 .

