^e May be conducted according to local protocols. ACTH test at screening is required if subject is not on glucocorticoid replacement therapy; morning (6:00:00:00AM) serum cortisol is < 15.0 µg/dL (measured at central laboratory), and if ACTH stimulation test or ITT (with serum cortisol measurements) performed within 90 days of screening is not available. Subjects who are not on glucocorticoid replacement therapy and are diagnosed with low morning cortisol may undergo an ACTH stimulation test at any time during the trial.

^f Only if MRI/CT scan within 6 months prior to screening is not available. MRI scan is required at Visit 7 for childhood cancer survivors. If DXA scan will be performed at the same visit, DXA scan should be conducted before MRI/CT scan that uses contrast.

^g Fundus photography is required for subjects with a diagnosis of diabetes mellitus at screening.

^h Blood draw should be between 6:00 and 10:00AM.

ⁱ Data reviewed by unblinded CRO team member; results not distributed to the trial site.

^j Results not distributed to the site.

^k An ADA sample will be collected at V7. An ADA sample and a pregnancy sample for females of childbearing potential will be collected approximately atleast 30 days after the last study drug dose for subjects not continuing into the extension trial.

^l DXA assessment windows: Up to 1 week prior to Visit 1, pre-dose; Up to 1 week before or after Visit 4 (Weeks 11, 12, 13); Up to 1 week after Visit 7 (Week 38 or Week 39). Body composition to be assessed at all DXA scans. Total body bone mineral content and bone mineral density to be assessed only at Visit 1. For subjects in Germany Visit 1 DXA will not be performed

^m As V2, V3 and V4 will be performed 4-5 days after injection for the once-weekly treatment arms, at these visits it will be assessed if scheduled up-titration can be performed and subjects will be instructed about the dose for further administration, starting with next injection 2-3 days after the visit.

ⁿ PRO completion on site by subject The order of PRO completion is: [REDACTED]

^o Not required if visit is conducted over the phone. The Subject Diary content cannot be reviewed but should be discussed.

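### The screening DXA scan is left out of the primary and key secondary models wherever a Visit 1 scan exists; adding it as a second covariate is a small, nearly free gain in precision

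*SAP*

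**What the plan says.** Protocol 10.2.1 lists a centrally read DXA scan among the screening assessments for all subjects. Exclusion criterion 18 in Protocol 8.1.2 rules out "Inability to undergo scanning by DXA or a non-interpretable DXA scan at screening", so a usable screening scan should exist for everyone randomised.

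Table 5 in Protocol 10.2.2 then schedules further scans: "At Visits 1, 4 and 7; central reading. DXA scan at Visit 1 is not applicable for Germany". The Visit 1 window is "Up to 1 week prior to Visit 1, pre-dose". The same table states "Body composition to be assessed at all DXA scans" and asks for the same machine throughout. The schedule in SAP section 2 repeats the exception: "For subjects in Germany Visit 1 DXA will not be performed".

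SAP 9.5 defines the DXA baseline: "The baseline value is defined as the last measurement on or before the first administration date (if time is not available) of the study drug". That is the Visit 1 scan in most countries and the screening scan in Germany. SAP 12.10.1 uses this value to form the change and as the ANCOVA covariate. SAP 12.10.2 repeats the model for trunk fat mass and total body lean mass. Neither document uses the screening value in these models when a Visit 1 scan exists.

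**The concern.** A single DXA reading contains scan error, and error in the baseline reading passes into the residual variance of the primary endpoint and of both alpha-protected secondaries. A second pre-dose reading of the same quantity, already taken and centrally read, carries information about the subject's untreated state that the model ignores. Two features make it suitable as a covariate. Inclusion criterion 8 requires a stable diet and exercise pattern, with no weight-reduction programme in the 90 days before or through screening. And eligibility depends on the screening scan being interpretable, not on its trunk fat value, so the scan brings in no selection effect.

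At stake is some precision in three analyses, at almost no cost.

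**Working it through.** **Inputs.** From SAP section 5 and Protocol 14.2: 80 per arm, difference 1.9, common SD 3.7, two-sided alpha 0.05. Assumed, because the documents do not give them: scan-error SD s of 0.5 to 2.0 points, independent between scans; true between-subject SD τ of 5 or 8 points; 3.7 taken as the SD of change from a single baseline scan.

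**1. The plan's own figure.** Power = Φ(1.9 / (3.7 × √(2/80)) − 1.96) = Φ(3.248 − 1.96) = 90.1%. The t-based version gives 89.8%. The stated 90% reproduces.

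**2. Change-score approximation.** The single-scan variance is 3.7² = 13.69, of which s² comes from the baseline scan. Two equally good scans reduce that part to s²/2, so the variance becomes 13.69 − s²/2.

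| s | variance | SD | reduction | power, 80 per arm | n per arm for 90% |
|---|---|---|---|---|---|
| 0.5 | 13.565 | 3.68 | 0.9% | 90.4% | 79 |
| 1.0 | 13.190 | 3.63 | 3.7% | 91.1% | 77 |
| 1.5 | 12.565 | 3.54 | 8.2% | 92.4% | 74 |
| 2.0 | 11.690 | 3.42 | 14.6% | 94.0% | 69 |

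**3. ANCOVA cross-check.** With k baseline scans, residual variance = (τ² + 13.69 − s²) − τ⁴ / (τ² + s²/k). Entering two equally good scans as separate covariates leaves the same residual as entering their mean, so k = 2 describes the second-covariate model. Example, τ = 8 and s = 1: 76.69 − 4096/65 = 13.675 with one scan, and 76.69 − 4096/64.5 = 13.186 with two, a fall of 3.6%. Over τ = 5 and 8 the falls are 0.9% (s = 0.5), 3.5–3.6% (s = 1.0), 7.3–7.9% (s = 1.5) and 12–14% (s = 2.0). These agree with step 2.

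**4. Cost of the extra covariate.** One degree of freedom costs roughly 1/N of the variance: 1/160 = 0.6% on the two weekly arms, or 1/240 = 0.4% if the daily arm is in the model. At s = 0.5 this uses up about half of the 0.9% gain or more.

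**5. German share.** Subjects with one scan gain nothing, so with share g the reduction is about (1 − g) times the figures above. The documents do not give g. As an illustration, g = 0.2 turns 3.6% into 0.8 × 3.6% = 2.9%.

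**6. If the scans are not equally informative.** Take an observed SD of 8. The correlation of the Visit 1 scan with Week 38 is then ρ₁ = 1 − 13.69/(2 × 64) = 0.893. Let the screening scan correlate 0.02 or 0.04 less (ρ₂), and let the two scans correlate at r = 0.95 or 0.97. Residual variance relative to the current plan is:
- mean of two scans, (1 − c²)/(1 − ρ₁²) with c = (ρ₁ + ρ₂)/√(2(1 + r)): 0.99 to 1.12;
- two covariates, (1 − R²)/(1 − ρ₁²) with R² = (ρ₁² + ρ₂² − 2rρ₁ρ₂)/(1 − r²): 0.97 to 1.00.

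Averaging can therefore do worse than the current rule. A second covariate cannot, apart from the degree of freedom in step 4.

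**The case against.** The last value before first dose is a conventional baseline. It is pre-specified, the same in all arms and consistent with the general rule in SAP 9.1. Table 5 of the Protocol also treats Visit 1 as the reference scan, since later scan times are matched to it. The screening scan is not wasted: it settles eligibility, supplies the German baseline and serves as a fallback if the Visit 1 scan is missing. All of this stands, and it is why the point is an option for improvement and not a defect.

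The scans may be up to about six weeks apart, and inclusion criterion 8 constrains behaviour rather than trunk fat or hydration. This also stands. It is the reason to prefer the second-covariate form to an average.

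A reader might infer a much larger gain. If the two scans correlate at 0.95 and the observed between-subject SD is 10, averaging appears to cut residual variance by 17%, equivalent to 1/0.832, or about 20% more subjects. That combination implies s = 10 × √0.05 = 2.24 points. Scan error would then account for 2 × 2.24² ≈ 10 of the 13.69 units of change variance, about 73%. Nothing in the documents supports noise on that scale.

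A reader might also infer that the later German gap between baseline scan and first dose biases the result, or that using both scans would cure it. Neither follows. The baseline rule is the same in every arm within each country, so the gap is not a between-arm bias. Germany would still have one earlier scan after the change.

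**Conclusion.** The point holds as a modest efficiency gain. Outside Germany a centrally read pre-dose value is available for all three DXA endpoints, and the models do not use it. Under independent scan errors of 0.5 to 1.5 points and stable body composition between scans, residual variance falls by about 1% to 8%. Power moves from 90.1% to about 90.4% to 92.4% before the small cost of one degree of freedom. At the low end the net gain is close to nil. It is smaller again in proportion to the German share and to any true change between scans. The sample-size statement is sound, the treatment comparison is unbiased under the current rule, and the plan is not deficient without the change.

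**What to change.** Keep the last-scan baseline and change score of SAP 9.5. Before unblinding, add the screening-scan value of the same DXA measure as a second baseline covariate in the ANCOVA (SAP 12.10.1 and 12.10.2) and in the imputation models (SAP 11.2.6) for trunk percent fat, trunk fat mass and total body lean mass. Add two rules:

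- Where only one pre-dose scan exists, as for all German subjects, set the second covariate equal to that value.
- For re-screened subjects, use only the scan from the final screening, because Protocol 15.2 allows re-screening after an adjustment of hormone replacement.

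Report a baseline defined as the mean of the two scans as a sensitivity analysis. The cost is SAP wording, programming of one covariate through the analyses that repeat the primary model, and about one degree of freedom; no new data are needed. The difference in baseline timing between Germany and other countries remains and should simply be acknowledged in SAP 9.5.
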